13.2 Interim Analysis

Blinded Phase:

No interim analysis is planned for this study. The blinded phase of this study will be locked and unblinded prior to completion of the OLE. The SAP covering the blinded phase will be finalized prior to unblinding the blinded phase.

Open-label Extension:

A cut of the OLE data will be used to support New Drug Application and Marketing Authorization Application filings. Further data cuts may be conducted as required.

Study Code: GWEP1521
EudraCT Number: 2015-002154-12
Protocol V8 23Apr19

13.3 Analysis Sets

Blinded Phase:

There will be up to three analysis sets in the blinded phase:

Intention to Treat (ITT)

- All patients who are randomized, receive IMP in the study and have post-baseline efficacy data will be included and analyzed according to their randomized treatment group.
- The ITT analysis set is the primary analysis set for all efficacy endpoints.

Per Protocol (PP)

If there are a sufficient number of significant protocol deviations in the study, a PP analysis set may also be presented.

- All patients who complete the study with no protocol deviations deemed to compromise the assessment of efficacy will be included and analyzed according to the treatment group they were randomized. The rules determining the PP analysis set will be fully defined prior to unblinding of the database.

Safety

All patients who received at least one dose of IMP in the study will be included and analyzed according to the treatment received. Only patients for whom it has been confirmed that they did not take any IMP will be excluded from this safety analysis set.

Open-label Extension:

There will be one analysis set in the open-label extension phase:

Safety

All patients who received at least one dose of IMP in the open-label extension phase of the study will be included. Only patients for whom it has been confirmed that they did not take any IMP in the OLE phase will be excluded from this safety analysis set.

13.3.1 Protocol Deviations

Protocol deviations will be listed and reasons for exclusion from the analysis populations will be summarized.

Study Code: GWEP1521
EudraCT Number: 2015-002154-12
Protocol V8 23Apr19

13.4 General Considerations

Unless stated otherwise, continuous variables will be summarized showing the number of non-missing values (*n*), mean, standard deviation, median, minimum and maximum and categorical variables will be summarized showing the number and percentage of patients falling in each category.

Unless otherwise specified, tables for the blinded phases will be summarized by randomized treatment group, and for the OLE phase will be summarized overall.

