2 OBJECTIVES

2.1 Primary

Blinded Phase:

To evaluate the efficacy of GWP42003-P as add-on therapy in reducing the frequency of seizures when compared with placebo in patients with tuberous sclerosis complex (TSC).

Open-label Extension:

To evaluate via the adverse events (AE) profile the long term safety and tolerability of GWP42003-P as add-on therapy in children and adults with TSC who experience inadequately-controlled seizures.

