9.1.2 Open-label Extension

Patients who successfully complete the blinded phase will be invited to participate in the OLE when they reach the End of Treatment visit (Visit 10) of the blinded phase. They will be issued with the OLE patient information and informed assent or the patient/parent(s)/legal representative information and informed consent (as applicable). Following adequate time to discuss the study with the investigator, nurse, relatives or caregiver, patients/parent(s)/legal representatives who provide written informed consent/assent at Visit B1 will be enrolled into the OLE. The OLE period will last for a maximum of 1 year; however, patients in the US and Poland may have the opportunity to continue in the OLE beyond this.

On-label use of mTOR inhibitors (for the treatment of seizures or tumors) and general anesthesia are permitted in the OLE phase of the trial.

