13.1 Sample Size, Power and Significance Levels

Blinded Phase:

A total of 210 patients will be enrolled. The 210 patients will be randomly allocated to one of four treatment groups (GWP42003-P 25 mg/kg/day, GWP42003-P 50 mg/kg/day, placebo 25 mg/kg/day dose volume equivalent, or placebo 50 mg/kg/day dose volume equivalent) at a 2:2:1:1 ratio. The placebo groups will be pooled for the analyses of efficacy.

If it is assumed that patients in the placebo group will experience a mean reduction in seizure frequency of 15% (from baseline), patients receiving GWP42003-P will experience at least a 50% reduction in seizures and a common standard deviation of 60%, then this sample size of 70 patients per group will be sufficient to detect a difference in response distributions with 90% power. This test is based on a two-sided non-parametric Wilcoxon-Mann-Whitney test for continuous response data with a 5% significance level.

Open-label Extension:

All patients who wish to continue on IMP following the blinded phase.

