13.6.2 Primary Endpoint(s)

Blinded Phase:

The primary endpoint is the change in number of seizures* during the treatment period (maintenance and titration) compared to baseline in patients taking GWP42003-P compared with placebo.

*Seizures include: focal motor seizures without impairment of consciousness or awareness; focal seizures with impairment of consciousness or awareness; focal seizures evolving to bilateral generalized convulsive seizures and generalized seizures (tonic-clonic, tonic, clonic or atonic) that are countable.

Data will be analyzed using negative binomial regression on the sum of the seizure counts during the treatment period. However, seizure frequency (average per 28 days) and percentage change in seizure frequency will be presented using summary statistics. A mixed effect model with repeated measures will be performed modelling the observed number of seizures in the baseline period and treatment period implemented within the framework of general linear models using the negative binomial response distribution. The model will include stratified age group (1–6 years, 7–11 years, 12–17 years and 18–65 years), time, treatment arm and treatment arm by time interaction as fixed effects and patient as a random effect. The log transformed number of days in which seizures were reported will be included as an offset. The time variable corresponds to an indicator for the baseline period and treatment period. The estimated ratio of least squares means for treatment period to baseline period and 95% confidence intervals (CIs) will be presented for each treatment arm. In addition, the estimated ratio of each GWP42003-P group to placebo and 95% CIs will be presented along with the p-value testing the null hypothesis that this ratio is 1.

The hypothesis testing approach for controlling the Type I error is described in [Section 13.6](#) and [Table 13.6-1](#).

If a patient withdraws from the study, then the primary analysis variable will be calculated from the available data, during the treatment period, prior to the patient withdrawing.

Open-label Extension:

The primary endpoint is the safety of GWP42003-P, evaluated by assessing the incidence, type and severity of AEs. Data will be presented as per [Section 13.6.5.2](#).

Study Code: GWEP1521
 EudraCT Number: 2015-002154-12
 Protocol V8 23Apr19

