13.6.5.2 Adverse Events

AEs will be coded according to the Medical Dictionary for Regulatory Activities dictionary.

A treatment emergent AE is one that started, or worsened in severity or seriousness, following the first dose of IMP.

Descriptive presentations of treatment emergent AEs will be given by preferred term and SOC for the safety analysis. The number of patients reporting at least one AE will be provided.

The following summaries will be produced:

- All-causality AEs.

Study Code: GWEP1521
EudraCT Number: 2015-002154-12
Protocol V8 23Apr19

- Treatment related AEs.
- All-causality AEs by severity.
- All-causality serious AEs.
- Treatment related serious AEs.
- AEs reported as leading to permanent cessation of study treatment.
- Fatal AEs.

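### The OLE's primary adverse-event results go into one overall column that mixes patients new to CBD with patients who completed 16 weeks on it

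*Protocol*

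**What the plan says.** The OLE's primary objective (Protocol, Section 2.1) is "To evaluate via the adverse events (AE) profile the long term safety and tolerability of GWP42003-P as add-on therapy". Section 13.6.2 gives the matching endpoint: "The primary endpoint is the safety of GWP42003-P, evaluated by assessing the incidence, type and severity of AEs". It refers to Section 13.6.5.2 for the presentation.

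Section 13.4 sets the default layout: "Unless otherwise specified, tables for the blinded phases will be summarized by randomized treatment group, and for the OLE phase will be summarized overall". Section 13.3 defines one OLE analysis set, the safety set: "All patients who received at least one dose of IMP in the open-label extension phase of the study will be included".

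Entry is governed by Section 9.1.2: "Patients who successfully complete the blinded phase will be invited to participate in the OLE". Section 4.1 describes the blinded transition. Patients from placebo titrate from zero to 25 mg/kg/day, those from 25 mg/kg/day continue at that dose, and those from 50 mg/kg/day taper to 25. Section 8.1.2 then allows all of them to titrate towards 50 mg/kg/day.

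**The concern.** Three groups with different histories enter one column. For placebo-origin patients, the transition and titration are their first exposure to CBD. For the 25 mg/kg/day group, the only new exposure is the step above 25. For the 50 mg/kg/day group, the OLE is continuation and re-exposure.

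The groups are also selected differently. Patients on CBD who met the mandatory transaminase withdrawal criteria in Section 10, or who left because of AEs, do not reach the OLE. Placebo-origin patients have not been through that filter for CBD.

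The column is the main display of the OLE's primary endpoint, and Section 13.2 says a cut of the OLE data will support marketing applications. A reader of that table could not tell whether a rate belongs to people starting CBD or to people already established on it. The first-exposure events of the placebo-origin patients, up to 70 people, are not separable in any table that the protocol specifies.

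**Working it through.** **1. Is the default overridden anywhere?**
- Section 13.3: one OLE safety set, all origins together.
- Section 13.6.2 (OLE): refers to 13.6.5.2, with no split.
- Section 13.6.5: separates the two placebo volume cohorts, but expressly for the blinded phase.
- Section 13.6.5.2: lists the AE summaries, with no columns by prior arm.

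So the overall layout in 13.4 is what the protocol prescribes for OLE AEs.

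**2. Who is in the column?** Section 13.1 gives 210 patients at 2:2:1:1. 210 × 2/6 = 70 in each active group, and 210 × 1/6 = 35 in each placebo group. This reproduces the stated 70 per group after pooling placebo. The share randomized to CBD is 140/210 = 66.7%.

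That is the share at randomization. OLE entry needs completion and consent, and the protocol gives no entry rates. Under assumed rates, the CBD-experienced share is:

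| Entry 25 / 50 / placebo | Patients entering | CBD-experienced share |
|---|---|---|
| 100 / 100 / 100% | 70 + 70 + 70 | 66.7% |
| 90 / 85 / 95% | 63 + 59.5 + 66.5 | 64.8% |
| 80 / 70 / 95% | 56 + 49 + 66.5 | 61.2% |
| 70 / 60 / 100% | 49 + 42 + 70 | 56.5% |
| 95 / 95 / 85% | 66.5 + 66.5 + 59.5 | 69.1% |

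It is a majority in each scenario, but two thirds exactly only if entry is equal.

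**3. How far can the overall figure lie from the new-starter figure?** Let s be the placebo-origin share and k the ratio of OLE incidence in prior CBD users to that in new starters. Then overall = s × p_new + (1 − s) × k × p_new, so overall/p_new = s + (1 − s)k. With s = 1/3, and an assumed 30% in new starters as illustration:

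| k (assumed) | overall / new | Overall column reads |
|---|---|---|
| 0.5 | 0.67 | 20% |
| 0.75 | 0.83 | 25% |
| 1.0 | 1.00 | 30% |
| 1.25 | 1.17 | 35% |

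**4. Does the uncertain share change this?** At k = 0.5 and the highest placebo share above (1 − 0.565 = 0.435): 0.435 + 0.565 × 0.5 = 0.72. At the lowest (1 − 0.691 = 0.309): 0.309 + 0.691 × 0.5 = 0.65. The result depends mainly on k, which the protocol does not inform.

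**5. Would a separate new-starter column be usable?** The 95% half-width is 1.96 × √(0.3 × 0.7/n) at an assumed 30% incidence. It is 10.7 points for n = 70, 11.6 for n = 60 and 12.7 for n = 50.

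**The case against.** **The rule is only a default.** Section 13.4 allows exceptions and Section 13 announces a SAP, which is not at hand. Column layout is often settled there, and no data are lost: AE dates are collected (Section 12.6) and allocation is held. This stands as a reason to give the point modest weight. It does not remove it, because the protocol states a positive rule for the OLE's primary endpoint. The wording permits a split without supplying one.

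**The OLE asks about long-term safety, not first exposure.** First-exposure AEs are tabulated by randomized group in the blinded phase, with 140 planned CBD patients and concurrent placebo. That is stronger evidence than an uncontrolled column of at most 70. This largely stands, and limits the point to the OLE tables. Even so, the mixed column is not a clean long-term figure either.

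**A reader might infer more:** that the overall figure understates AE incidence in newly treated patients, and that this incidence cannot be read at all. The documents do not support that.
- They give no AE rates by prior exposure, so the direction is an assumption.
- Selection for tolerance is only partial: Section 8.1.2 lets a poorly tolerated dose be reduced temporarily or permanently, so such patients can complete and enter.
- The step above 25 mg/kg/day is new exposure for the 25 mg/kg/day group, so a uniformly low rate in prior users cannot be presumed.
- First exposure in the active arms remains visible in the blinded-phase tables.

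**Treatment emergence.** Section 13.6.5.2 says "A treatment emergent AE is one that started, or worsened in severity or seriousness, following the first dose of IMP", and IMP includes placebo, so the anchor does not mark the first CBD dose in placebo-origin patients. In practice this matters little: an AE that starts in the OLE is treatment-emergent under either anchor.

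**Conclusion.** The point holds as a gap in how the OLE's primary safety result is presented. The prescribed single column combines CBD-naive and CBD-experienced patients, and if their AE incidences differ in either direction the overall figure misdescribes both without showing it.

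The size cannot be fixed from the protocol. Over assumed prior-to-new ratios of 0.5 to 1.25, with one third new starters, the overall figure runs from 0.67 to 1.17 times the new-starter incidence, and there is no distortion at a ratio of 1. Understatement occurs only if prior-CBD completers have lower OLE rates, which is plausible from selection and adaptation but is not shown. The one-third share itself assumes equal entry from all arms.

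The weight is modest. Blinded-phase efficacy and safety conclusions are untouched, and the information needed for a better table will already have been collected.

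**What to change.** Amend Sections 13.4 and 13.6.5.2 so that OLE AE summaries are presented by prior randomized group (pooled placebo, 25 mg/kg/day, 50 mg/kg/day) alongside the overall column.

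This needs no new data. Section 13.2 has the blinded phase locked and unblinded before the OLE is complete, so allocation will be available. The price is a few extra columns with smaller denominators: at most about 70 CBD-naive patients, with the precision worked out above.

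Two additions are secondary. One sentence could state which first dose defines treatment emergence in the OLE. An integrated, exposure-adjusted AE table counted from each patient's first dose of GWP42003-P would be informative but is optional.

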13.5 Accountability and Background Characteristics

13.5.1 Enrollment and Disposition

All patients (screened, enrolled/randomized, prematurely terminated IMP) will be accounted for in the enrollment and disposition summary tables.

13.5.2 Baseline and Demographic Characteristics

Age, sex, ethnic origin (as allowed per local regulations) and any other demographic or baseline characteristics, including history of epilepsy and epilepsy-specific genetic testing, will be summarized, using appropriate summary statistics.

13.5.3 Medical History

Previous and current medical conditions will be summarized by System Organ Class (SOC), including details of epilepsy.

13.5.4 Concomitant Medication

Concomitant medications (including standard AED and rescue medication) taken prior to and during the study will be summarized separately, by medication class and active ingredients.

13.6 Endpoints and Statistical Methods

Blinded Phase:

Statistical hypothesis testing will be performed on the primary endpoint and other endpoints as appropriate. Each endpoint, including the primary will have 2 comparisons against placebo (25 mg/kg/day GWP42003-P and 50 mg/kg/day GWP42003-P vs. placebo). Also, 3 key secondary endpoints have been defined.

Study Code: GWEP1521
 EudraCT Number: 2015-002154-12
 Protocol V8 23Apr19

The primary and key secondary endpoints will be tested with their Type I error controlled by use of a hierarchical gate-keeping procedure, in the sequence given in Table 13.6-1. One must reject the null hypothesis of an endpoint at the level of 0.05 (2-sided) to test the hypothesis of the subsequent endpoint in the sequence at the level of 0.05 (2-sided). If a null hypothesis is not rejected then testing will stop and all subsequent analyses will be declared not statistically significant.

Test	Endpoint	Treatment Comparison
1	Change from baseline in number of TSC-associated seizures	25 mg/kg/day GWP42003-P vs. Placebo
2	50% responder analysis	25 mg/kg/day GWP42003-P vs. Placebo
3	Change from baseline in number of TSC-associated seizures	50 mg/kg/day GWP42003-P vs. Placebo
4	50% responder analysis	50 mg/kg/day GWP42003-P vs. Placebo
5	Change in CGIC/SGIC	25 mg/kg/day GWP42003-P vs. Placebo
6	Change from baseline in total seizures	25 mg/kg/day GWP42003-P vs. Placebo
7	Change in CGIC/SGIC	50 mg/kg/day GWP42003-P vs. Placebo
8	Change from baseline in total seizures	50 mg/kg/day GWP42003-P vs. Placebo

13.6.1 Evaluable Period

Blinded Phase:

The start of the evaluable period of the study (Day 1) is defined as the first day the patient took IMP, as recorded on the CRF, or the day of randomization if this date is unknown.

The end of the evaluable period is defined as the earliest of:

- Day 113 of treatment for the IVRS reported efficacy data and the day of Visit 10 for the CRF-based efficacy data;
- The last day on which study IMP was taken (as stated on the study outcome CRF) for the IVRS reported efficacy data and the day after this for the CRF-based efficacy data;
- The day before a relevant change in prohibited or AED medications was made.

Open-label Extension:

All data collected during this phase will be summarized across time, using appropriate descriptive statistical methods. Changes from pre-randomization baseline will also be presented. Treatment compliance and exposure to treatment will also be summarized.

Study Code: GWEP1521
EudraCT Number: 2015-002154-12
Protocol V8 23Apr19

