8.2 Concomitant Therapy

It is theoretically possible that GWP42003-P may modify the metabolism of other drugs (including AEDs) administered concurrently and there remains the possibility of pharmacological interactions between GWP42003-P and other concurrently administered drugs. Doses of any concomitant AEDs must have been stable for at least four weeks prior to screening and must remain stable throughout the blinded study period. If during the blinded or OLE phase plasma concentrations of concomitant AEDs are found to be altered following administration of IMP, or if there are side-effects suspected of being related to an elevation in the concomitant AED concentration, the investigator must contact the GW medical monitor to discuss best management. Decisions should be based on clinical symptoms and not plasma levels of AEDs. Further information on drug interactions can be found in the IB⁵¹.

Concomitant AED dose reductions are permitted on clinical grounds (e.g., due to AEs or transaminase elevations **not meeting** withdrawal criteria specified in [Section 10](#) and [Section 12.8](#)) following discussion with the GW medical monitor.

Study Code: GWEP1521
EudraCT Number: 2015-002154-12
Protocol V8 23Apr19

Additional new AEDs (including oral mTOR inhibitors) are not allowed to be added during the randomized phase of the trial but may be considered on a case-by-case basis for the OLE phase in accordance with local licensing and after consultation with the GW medical monitor.

The use of rescue medication is allowed when necessary. Any medication, other than the IMP, taken during the study must be recorded on the Case Report Form (CRF).

Any non-pharmacological therapies (e.g., ketogenic diet, vagus nerve stimulation) must also be stable up to four weeks prior to screening and throughout the duration of the study.

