8.3 Prohibited Therapy During Study Period

The following medications are prohibited for the duration of the study beginning from acquisition of patient consent/assent. However, any patients taking these medications after randomization should not be withdrawn from the study unless there are safety concerns. If applicable, the possible effects of these medications on the primary endpoint will be considered during the assessment of the evaluable period (see [Section 13.6.1](#)).

- Any new medications or interventions for epilepsy (including ketogenic diet and vagus nerve stimulation) or changes in dosage.
- Recreational or medicinal cannabis or synthetic cannabinoid-based medications (including Sativex[®]).
- Any other IMP taken as part of a clinical trial.

Care should be taken with drugs, or their metabolites, that are cytochrome P450 2C19 substrates, such as N-desmethyloclobazam. Care should also be taken with drugs, or their metabolites, that are solely or primarily metabolized by UDP-glucuronosyltransferase 1A9 and 2B7.

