9.2.11 Patient Diary

A diary will be completed daily throughout the study. Patients or their caregivers will be instructed on how to complete the diary and will be asked to record information daily. The number and type of seizures and the severity of focal seizures as well as information on AEs, concomitant AEDs and rescue medication will be collected each day from baseline (Visit 2). Information on IMP intake will also be recorded each day from randomization (Visit 3) until completion of dosing or withdrawal (Visit 10/Withdrawal visit).

Seizure information, including the number and seizure subtype, as well as the severity of focal seizures and the number of episodes of *status epilepticus* will be collected through an IVRS telephone diary completed daily throughout the blinded phase of the study by the patient or their caregiver. This IVRS telephone diary will be completed on a weekly basis during the OLE. The patient or their caregiver will also complete a paper diary daily to record AEs, concomitant AEDs, IMP intake and rescue medication throughout the study.

The following seizure subtypes will be collected daily in the IVRS telephone diary:

- Focal motor seizures without impairment of consciousness or awareness[#]
- Focal seizures with impairment of consciousness or awareness[#]
- Focal seizures evolving to bilateral generalized convulsive seizures[#]
- Generalized seizures:
 - Tonic-clonic[#]
 - Tonic[#]
 - Clonic[#]
 - Atonic[#]
- ‘Other’ seizures:
 - Absence seizures^{**}
 - Myoclonic seizures^{**}

Study Code: GWEP1521
EudraCT Number: 2015-002154-12
Protocol V8 23Apr19

- Focal sensory seizures **
- Infantile/epileptic spasms **
- Episodes of status epilepticus

To be included in primary seizure endpoint.

** To be included in composite 'other' seizure count.

For the purposes of calculating the composite seizure score, the severity of focal seizures will be assessed according to the following criteria:

- Type 1 - Focal motor seizures without impairment of consciousness or awareness.
- Type 2 - Focal seizures with impairment of consciousness or awareness.
- Type 3 - Focal seizures evolving to bilateral convulsive seizures.

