10 WITHDRAWAL

In accordance with the Declaration of Helsinki⁵⁶, the ICH Tripartite Guideline for GCP Topic E6(R2)⁵², the U.S. FDA regulations relating to good clinical practice and clinical trials^{57,58,59}, the European Union (EU) Clinical Trials Directive⁶⁰, the EU Good Clinical Practice (GCP) Directive⁶¹ and/or other applicable regulations, a patient has the right to withdraw from the study at any time and for any reason without prejudice to his or her future medical care by the physician or at the institution.

The patient must be withdrawn from the study if any of the following apply:

- Administrative decision by the investigator, GW, or a Regulatory Authority.
- Pregnancy.
- Protocol deviation that is considered to compromise potentially the safety of the patient.
- Withdrawal of patient consent/assent.
- Withdrawal of parent(s)/legal representative consent.
- ALT or AST > 3 × ULN with the appearance of fatigue, nausea, vomiting, right upper quadrant pain or tenderness, fever, rash, and/or eosinophilia (> 5%).
- ALT or AST > 8 × ULN.
- ALT or AST > 5 × ULN for more than two weeks.
- ALT or AST > 3 × ULN **and** (TBL > 2 × ULN **or** INR > 1.5).
- Lost to follow-up.

Note: Prior to withdrawal for the transaminase elevations noted above, the investigator may choose to confirm the transaminase elevations by repeating the following laboratory tests within 24 to 48 hours: ALT, AST, TBL, INR, %eosinophils, gamma-glutamyl transferase and alkaline phosphatase. Should the above transaminase elevation criteria be confirmed, the patient must be withdrawn from the trial. In cases where the transaminase elevation withdrawal criteria are not met or confirmed, the dose of IMP or a concomitant AED with known hepatotoxicity should be reduced following discussion with the GW medical monitor.

Study Code: GWEP1521
EudraCT Number: 2015-002154-12
Protocol V8 23Apr19

Patients may also be withdrawn from the study for any of the following:

- Did not meet eligibility criteria.
- Patient non-compliance.
- AE (including clinically significant laboratory result) which, in the opinion of the investigator, would compromise the continued safe participation of the patient in the study.
- Suicidal ideation or behavior of type 4 or 5 during the treatment period, as evaluated with the C-SSRS.
- Any evidence of drug abuse or diversion.
- General anesthesia (blinded phase only).
- Addition of a new AED (blinded phase only).

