13.6.2.1 Sensitivity Analysis for the Primary Endpoint

Blinded Phase:

The following sensitivity analyses will be conducted for the primary endpoint for the blinded phase:

- Wilcoxon rank-sum test on percentage change from baseline in seizure frequency during the treatment period. An estimate of the median differences between each GWP42003-P group and placebo, together with approximate 95% CIs, will be calculated using the Hodges–Lehmann approach.
- Primary endpoint analysis repeated using the PP analysis set.
- Primary endpoint analysis repeated using the maintenance period (Day 29 to the end of the evaluable period) rather than the treatment period.
- Primary endpoint analysis repeated using the worst case of last observation carried forward (LOCF), next observation carried backward (NOCB) and the mean from the non-missing data for each patient to impute missing data arising from unreported days in IVRS.
 - Any intermittent missing data for the number of seizures arising from unreported days in IVRS will be imputed using the worst (highest number of seizures) of the following for each patient: LOCF, NOCB and the mean daily number of seizures during the treatment period based on non-missing data:

$$\text{Number of seizures} \div \text{Number of reported days in IVRS.}$$
- A rank ANCOVA on percentage change from baseline in number of seizures (average per 28 days) during the treatment period.
 - The ranks of the percentage change from baseline and the baseline number of seizures (average per 28 days) will be calculated. The rank of the percentage change from baseline will then be analyzed using an ANCOVA model with the rank of the baseline number of seizures (average per 28 days) and age group (1–6 years, 7–11 years, 12–17 years and 18–65 years) as covariates and treatment group as a fixed factor. The estimated least squares means, treatment differences, together with the 95% CIs and p-value will be presented.
- ANCOVA of log transformed number of seizures (average per 28 days) during the treatment period.

Study Code: GWEP1521
EudraCT Number: 2015-002154-12
Protocol V8 23Apr19

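### The seizure count stops the day before a relevant AED or prohibited-medication change, and no listed sensitivity analysis uses the daily counts that follow

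*Protocol*

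**What the plan says.** **The cut.** In Protocol Section 13.6.1 the evaluable period for IVRS efficacy data ends at the earliest of Day 113, the last day of IMP, or "The day before a relevant change in prohibited or AED medications was made". The word *relevant* is not defined.

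**The endpoint.** Section 13.6.2 states: "The primary endpoint is the change in number of seizures* during the treatment period (maintenance and titration) compared to baseline". Section 13.3 makes the ITT set primary for all efficacy endpoints. The model uses the log of the number of reported days as an offset.

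**Data after a change.** Section 9.2.11 says seizure information "will be collected through an IVRS telephone diary completed daily throughout the blinded phase of the study by the patient or their caregiver". Section 8.3 lists as prohibited "Any new medications or interventions for epilepsy (including ketogenic diet and vagus nerve stimulation) or changes in dosage", but adds that "any patients taking these medications after randomization should not be withdrawn from the study unless there are safety concerns". It leaves any effect on the primary endpoint to the assessment of the evaluable period.

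**AED changes that the protocol foresees.** Section 8.2 states: "Concomitant AED dose reductions are permitted on clinical grounds", with adverse events and transaminase elevations as examples. For transaminase elevations that fall short of mandatory withdrawal, or that repeat testing does not bear out, Section 10 says: "the dose of IMP or a concomitant AED with known hepatotoxicity should be reduced following discussion with the GW medical monitor". Section 9.2.9.2 provides for AED dose adjustment to hold plasma concentrations stable.

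**Sensitivity analyses.** Section 13.6.2.1 lists eight. One reads: "Primary endpoint analysis repeated using the maintenance period (Day 29 to the end of the evaluable period) rather than the treatment period".

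**The concern.** A change in AED dose after randomization can be a consequence of treatment. The reasons the protocol gives for such changes (adverse events, transaminase elevations, altered AED concentrations) are ones that IMP may itself produce, so changes could be more frequent in the active arms. If the seizure rate then differs from the rate before the change, removing those days shifts the arm's estimated rate by an amount that depends on how many patients are affected and when.

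The result would describe seizure frequency while background AEDs stay unchanged, whereas the endpoint is worded over the whole treatment period. The 50% responder and total-seizure tests in the hierarchy draw on the same IVRS data. A reader of the results would want to know whether the cut matters, and the listed analyses would not show it.

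**Working it through.** **1. The plan's own figure.** Section 13.1 gives 70 per group for 90% power, with reductions of 15% and 50%, SD 60%, and a two-sided 5% Wilcoxon-Mann-Whitney test. With Noether's formula, θ = Φ(35/(60√2)) = 0.660. The total is N = (1.960 + 1.282)²/(3 × 0.160²) ≈ 136.8, or 68.4 per group, so 69. Power at 70 per group is 90.6% by this formula and 91.7% in 20,000 simulated trials. The figure reproduces, and the present point does not depend on it.

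**2. Does any listed analysis use the later days?**

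| Analysis in 13.6.2.1 | What it changes |
|---|---|
| Wilcoxon; rank ANCOVA; log ANCOVA | Method only |
| Per protocol | Narrows the analysis set |
| Maintenance period | Window, expressly ending with the evaluable period |
| Each 4 weeks of maintenance | Window; nothing said about days after the evaluable period |
| Worst of LOCF, NOCB and mean | Fills unreported IVRS days |
| Multiple imputation | Imputes, with MNAR tied to discontinuation |

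None is specified to use counts observed after the change.

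**3. Size, for illustration.** From Section 13.1: rates relative to baseline of 0.50 (active) and 0.85 (placebo), ratio 0.50/0.85 = 0.588, ln(0.588) = −0.531. Assumed, because the protocol gives no figures: a share *f* of active patients have a relevant change; day *d* is their last counted day; their rate is then multiplied by *r*; placebo is unaffected.

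The offset removes days together with counts, so the truncated analysis still estimates 0.588. With all days to Day 113:

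all-data ratio = 0.588 × [1 + (r − 1)(113 − d)/113]^f

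The days lost are 84/113 = 0.743 for d = 29 and 56/113 = 0.496 for d = 57.

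| f | d | r | Bracket | All-data ratio | Shift as share of 0.531 |
|---|---|---|---|---|---|
| 10% | 57 | 1.5 | 1.248 | 0.601 | 4% toward no effect |
| 20% | 29 | 1.5 | 1.372 | 0.627 | 12% toward no effect |
| 30% | 29 | 2.0 | 1.743 | 0.695 | 31% toward no effect |
| 20% | 29 | 0.8 | 0.851 | 0.570 | 6% away from no effect |
| 30% | 29 | 0.8 | 0.851 | 0.561 | 9% away from no effect |

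The last column is f × ln(bracket)/0.531. Over the grid of f from 5% to 30%, d = 29 or 57, and r from 0.8 to 2.0, the all-data ratio runs from 0.561 to 0.695.

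**4. Check.** A simulation of patient-level log rates stood in for the negative binomial mixed model (70 per arm, 400 runs per setting, f from 10% to 30%, 2% of placebo patients also changed). Truncated ratios were 0.583 to 0.595 and all-data ratios 0.561 to 0.693.

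**The case against.** **Truncation is discretionary.** Only a *relevant* change triggers it, and Section 8.3 implies case-by-case assessment. A dose reduction permitted by Section 8.2 is nowhere said to be relevant, and Section 13.6.2 does not name the evaluable period; the link comes from Sections 8.3, 13.6.1 and 13.6.2.1. This stands: one cannot say that every patient whose AED is reduced for toxicity loses later seizures.

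**Direction.** A reader might infer that the rule overstates the drug effect, because active-arm days after an AED reduction should carry more seizures and placebo days after an added or raised AED fewer. The documents do not support that as a conclusion. The offset means bias needs a changed rate, and a reduction that corrects a raised AED level need not leave the patient under-treated. On the placebo side, Section 8.2 disallows new AEDs in this phase and Section 10 lists one as a possible reason for withdrawal, so some of the supposedly discarded data may not exist.

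**Estimand.** The design requires stable background AEDs, and ending the count when they change is a defensible way to isolate add-on efficacy. This stands against rewriting the primary rule. Keeping days after AED reductions but dropping those after increases would also be asymmetric.

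**SAP territory.** Section 13.6.3 says further sensitivity analyses may be specified in the SAP, which is not at hand. That allows the missing analysis but does not secure it. The truncation rule and the list of analyses are fixed in the protocol.

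**Conclusion.** The concern holds in limited form. A post-randomization event that is plausibly related to treatment can end a patient's primary seizure count while daily reporting continues, and no listed sensitivity analysis would show the consequence. The effect on the treatment ratio may be negligible or material: about 0.56 to 0.70 with all data against 0.588 with the cut, and on either side of it. That range rests on assumed shares of patients, timings and rates after the change; only the 50% and 15% reductions come from the protocol. It shows what is possible and is not an estimate of bias. The primary analysis need not change. One all-data rerun is a cheap improvement that would settle whether the cut drives the result.

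**What to change.** Keep the evaluable-period rule for the primary analysis, and:

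1. Add to Section 13.6.2.1 a repeat of the primary endpoint analysis on all IVRS seizure data reported from Day 1 to Day 113 or withdrawal, regardless of any change in AED or prohibited medication. Do the same for the 50% responder analysis.
2. Tabulate by arm the number of patients truncated under the third criterion of Section 13.6.1 and the days lost.
3. Define before unblinding which changes count as relevant for truncation.
4. Reconcile Sections 8.2, 8.3, 9.2.9.2 and 10. Changes in dosage of epilepsy medication are listed as prohibited in one place and permitted or called for in others. Section 8.2 bases decisions on clinical symptoms and not plasma levels, whereas Section 9.2.9.2 adjusts doses to keep concentrations stable. Which clinical rule is right is for the sponsor to decide.

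The cost is wording, a small table and one extra run of each of the two analyses on data already collected. The all-data estimate will include the effect of changed AEDs and may be slightly less favourable to the drug.
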